Acupuncture is a non-pharmacologic modality that involves insertion of filiform needles into certain points on the body, followed by manual manipulation, heat, or electrical stimulation to elicit therapeutic effects. Numerous randomized controlled trials have shown its effectiveness in pain management. A systematic review of 17 trials (N= 2,027) showed that acupuncture reduced the intensity of acute and chronic low back pain more than sham acupuncture, leading ACP's clinical practice guidelines to recommend acupuncture. In a meta-analysis of 20,827 patients from 39 RCTs, the analgesic effect size of acupuncture was

0.5 SDs compared with no acupuncture control and close to 0.2 SDs compared with sham. Neuroscience research has shown that acupuncture increases production of endogenous analgesic neurotransmitters, such as endorphins and adenosine. In January 2020, Centers for Medicare & Medicaid Services (CMS) finalized a decision to cover acupuncture for Medicare patients with chronic low back pain. We conducted a pilot randomized study showing that acupuncture during HiChemo/HSCT has the potential to be an opioid-sparing non-pharmacologic therapy that significantly reduces opioid use and opioid side effects without compromising pain control. We found that patients in the sham acupuncture group had greater than five times the odds of increasing pain medications from baseline compared with those in the true acupuncture group (OR 5.31, 95% Confidence Interval (CI) 1.35 to 20.93, P=0.017). The effect was most pronounced among patients who were not taking opioids at baseline ("opioid-naïve"). In those patients, any increase in opioid use was due to the pain induced by HiChemo/HSCT, rather than from pre-existing pain. Among opioid-naïve patients, 20% (4 of 20) of those who received sham acupuncture started to use opioids during HiChemo/HSCT (Day 5), 40% around Day 30, and 25% became long-term opioid users (Day 90). In contrast, among the 15 patients who received true acupuncture, none needed to use opioids on Day 5 (p=0.119) or Day 30 (p=0.006), and only one (7%) became a long-term opioid user (Day 90, p=0.365). Acupuncture also reduces symptoms commonly associated with opioid use, such as nausea, poor appetite and drowsiness. The proposed study expands on that research and uses a patient-centered approach to address this gap in the evidence.

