In our pilot study, among “opioid-naïve” patients, 25% of sham acupuncture (SA) patients and 7% of true acupuncture (TA) patients were opioid users at Day 90. For our sample size/power estimates for Aim 1, we conservatively assume that patients in the OPI arm will have similar Day 90 opioid usage (25%) as the SA patients in our prior study, and that 10% of patients in the ACU arm will be using opioids at Day 90 (slightly higher than the TA arm in our pilot study). This translates to a relative reduction of 60% fewer opioid users in the ACU arm, and an odds ratio of 0.33, which would be considered clinically meaningful. The attrition rate was only 5% in our pilot study. However, we will conservatively plan for a high 10% attrition rate by randomizing 300 patients (150 per arm) in order to obtain 270 patients (135 per arm) with evaluable Day 90 endpoints. With an initial sample size of 300 patients and a 10% attrition rate, we will have 81% statistical power to detect this Day 90 difference between the two arms (i.e. 10% vs 25%) at a significance threshold of  $p<0.02$  using logistic regression analysis and a two-sided significance test. It is possible that the OPI group will have higher opioid use than the SA patients in our pilot study, as sham acupuncture is known to have some placebo effect. We therefore expect a larger effect size than we observed in the pilot study where true acupuncture was compared to sham acupuncture. In that scenario, assuming 30% in the OPI group use opioids versus 10% in ACU group, our power will increase to 96%.

We based our sample size exclusively on having adequate power for the Day 90 comparison of opioid use. This was due to the high public health priority to find pain interventions that can reduce long-term opioid use. That said, we expect the Day 7 comparison to have similar power as the Day 90 comparison. We believe this is a conservative assumption, and that we most likely have higher power at Day 7 due to lower attrition and potentially a larger effect size at Day 7 relative to Day 90. For example, in our pilot study, 20% of sham acupuncture (SA) patients were using opioids at Day 5 (opioid usage not collected at Day 7) compared to none of the true acupuncture (TA) patients.

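### Section 3.0's pilot Day 90 sham rate of 25% and its p-value of 0.365 cannot both be right on the printed patient numbers, and Section 14.1 uses that 25% to size the trial

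*Combined protocol and SAP*

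**What the plan says.** Section 3.0 (Background and Rationale) gives the pilot results for patients not on opioids at baseline.

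- Sham arm, Day 5: "20% (4 of 20) of those who received sham acupuncture started to use opioids during HiChemo/HSCT (Day 5").
- Sham arm, later: "40% around Day 30, and 25% became long-term opioid users (Day 90").
- The comparison is "among the 15 patients who received true acupuncture". In that group "none needed to use opioids on Day 5 (p=0.119) or Day 30 (p=0.006"), and at Day 90 "only one (7%) became a long-term opioid user (Day 90, p=0.365").

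Section 14.1 (Sample Size Considerations) repeats the 25% and 7%. It takes 25% as the OPI planning rate, assuming "similar Day 90 opioid usage (25%) as the SA patients in our prior study", and describes the assumption as conservative. It sets the ACU rate at 10%, a little above the pilot. With 300 randomized, 10% attrition, 135 evaluable per arm and a two-sided threshold of 0.02, it says "we will have 81% statistical power to detect this Day 90 difference between the two arms (i.e. 10% vs 25"%). It states that the sample size rests only on the Day 90 comparison. The one alternative scenario goes upward: 30% against 10%, with 96% power. No OPI rate below 25% is shown.

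**The concern.** A p-value for a two-by-two table is fixed by the four counts and the test. Section 3.0 prints enough to recover both, so the three p-values can be checked. Two agree with their counts and the Day 90 one does not.

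In most protocols this would be a background slip. Here the percentage in question is carried into Section 14.1 as the OPI rate in the only calculation that sized the trial. If the 25% is the faulty figure, the pilot support for the planning rate is one patient in 20 weaker than stated. The description of that rate as conservative then loses its basis, and a reader has no power figure for the rate the pilot actually showed.

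**Working it through.** **Inputs.** Section 3.0: 20 sham and 15 true-acupuncture patients; sham users 4/20 at Day 5, 40% (8/20) at Day 30 and 25% (5/20) at Day 90; true-acupuncture users 0, 0 and 1; p = 0.119, 0.006 and 0.365. Section 14.1: 135 evaluable per arm, two-sided alpha 0.02, OPI 25%, ACU 10%, power 81%.

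**Step 1: identify the test.** Two-sided Fisher's exact test:

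| Day | Table | Fisher p | Printed p |
|---|---|---|---|
| 5 | 4/20 v 0/15 | 0.1186 | 0.119 |
| 30 | 8/20 v 0/15 | 0.0056 | 0.006 |
| 90 | 5/20 v 1/15 | 0.2072 | 0.365 |
| 90, if 4 sham users | 4/20 v 1/15 | 0.36497 | 0.365 |

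The Day 90 values come from adding the hypergeometric probabilities no larger than that of the observed table.

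- Six users among 35 patients, five of them sham: 0.14328 + 0.02388 (six sham) + 0.03700 (one sham) + 0.00308 (none) = 0.2072.
- Five users among 35, four of them sham: 0.22387 + 0.04776 (five sham) + 0.08410 (one sham) + 0.00925 (none) = 0.3650.

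**Step 2: could another test or missing values explain it?** For 5/20 v 1/15, chi-square gives 0.154, the Yates-corrected version 0.332 and a Wald logistic test 0.183. None is 0.365. A search over sham denominators 6-20, true-acupuncture denominators 8-15 and 0-2 true-acupuncture users finds two tables whose Fisher p rounds to 0.365: 4/20 v 1/15, and 4/12 v 2/14. The second contradicts the single true-acupuncture user that Section 3.0 reports. The nearest tables with 25% sham users are 5/20 v 1/14 (0.3636) and 5/20 v 1/13 (0.3644). Both round to 0.364, and both depart from the printed 15.

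**Step 3: reproduce the plan's power.** With n = 135 and z = 2.326:

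- Pooled test of proportions: power = Φ{[(p1 − p2) − z√(2p̄(1 − p̄)/n)] / √([p1(1 − p1) + p2(1 − p2)]/n)}. For 25% v 10%: Φ[(0.15 − 0.1076)/0.0453] = 82.5%.
- Wald test of the log odds ratio: power = Φ(|log OR|/SE − z). For 25% v 10%: Φ(1.0986/0.3490 − 2.326) = 79.4%.

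The stated 81% lies between these. The 96% for 30% v 10% also reproduces (96.7% pooled, 94.6% Wald).

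**Step 4: power if the OPI rate were 20%.** Same n and alpha:

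| ACU rate | Reason for that rate | Pooled | Wald |
|---|---|---|---|
| 10% | plan's ACU rate kept | 49.0% | 47.4% |
| 8% | plan's 60% relative reduction kept (0.20 × 0.40) | 69.9% | 66.6% |
| 7.7% | plan's odds ratio of 0.33 kept | 72.9% | 69.3% |
| 6.7% | pilot rate, 1/15 | 82.0% | 77.5% |

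For 20% v 10%, other methods (continuity-corrected, exact Fisher, unpooled, arcsine, log odds ratio with null variance) widen the range to 42-52%.

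**The case against.** The strongest defence is that nothing in Section 14.1 is miscalculated. The 81% follows from its stated inputs, and the pilot p-value is not one of them. That stands.

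A reader might infer that the trial's real power is 49% and not 81%. The documents do not support this, for three reasons.

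1. They do not show that the 25% is the faulty figure. It appears consistently in Sections 3.0 and 14.1, while p=0.365 appears once. Four of 20 is also the printed Day 5 sham count, so carrying that count into the Day 90 test by mistake would give 0.365 with 25% still correct. One missing true-acupuncture value would come within about 0.001 of the printed p-value. That is an assumption; it conflicts with the printed 15, although Section 14.1 does say "The attrition rate was only 5% in our pilot study".
2. The 49% is the least favourable scenario. It lowers the OPI rate to 20% but keeps an ACU rate deliberately set above the pilot, which shrinks the relative reduction from 60% to 50%. With both pilot rates, 4/20 and 1/15, power is 77-82%, close to the stated 81%.
3. Section 14.1 gives a separate reason for a higher OPI rate: usual care lacks any placebo effect of sham. A 25% planning rate could be defended on that ground even if the sham rate was 20%.

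The dispute is also over one patient in 20. The exact 95% intervals, 6-44% for 4/20 and 9-49% for 5/20, overlap almost entirely. None of this removes the contradiction in Section 3.0, where one printed figure has to change.

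**Conclusion.** The contradiction is established, given the printed denominators of 20 and 15 and the Fisher test that reproduces the other two p-values. Its consequence for the sample size is conditional. If the pilot count was 5/20, only a background p-value is wrong and the power statement is untouched. If it was 4/20, the planning rate loses its stated source, and power at 20% depends on which ACU rate is assumed, from roughly half to roughly the plan's own figure. The documents cannot settle which case applies; the pilot data can. No endpoint, alpha, test or analysis set is affected, so this is a should-fix item.

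**What to change.** Check the pilot Day 90 counts and denominators, then make one of two edits.

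- **If 5/20 and 1/15:** change the Day 90 p-value in Section 3.0 to 0.21. Leave Section 14.1 as it is.
- **If 4/20 and 1/15:** change the sham rate to 20% in Sections 3.0 and 14.1. Stop presenting 25% as the pilot sham rate, or as conservative on that basis. It can stay as a planning rate only if the usual-care argument is given as its justification. Add Day 90 power at an OPI rate of 20% with 135 per arm and two-sided alpha 0.02: about 47-49% against 10% (42-52% across methods), 67-70% against 8%, and 77-82% against 6.7%.

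If the check shows a different denominator, print it and recompute the p-value from it.

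Keep the sample size at 300 in either case. The cost is one look-up in the pilot data and a few sentences. In the second case the reported power may look less favourable.

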## 14.2. Statistical Methods.

**14.2.1. General Approaches.** All analyses will be by intent-to-treat, with patients analyzed as randomized, irrespective of treatment actually received. Demographics and other relevant variables (e.g., number of acupuncture sessions received in the ACU arm) will be summarized by treatment arm using standard descriptive statistics. All data at all assessment time points will be summarized by treatment arm using standard descriptive statistics and plotted to visually assess trajectories over time. In the following subsections, we present specific analysis plans that are tailored to address our specific aim hypotheses, focus on single assessment time points, have relatively straightforward interpretations, and will be used to draw our primary conclusions regarding the Aims of this trial. However, our more general analysis approach will use more complex models to capitalize on the longitudinal nature of the study design and allow us to examine plots of the model-based trajectories of our outcome measures over time by study arm, giving us a visual overview of each outcome measure that incorporates all of the available data. For Aim 1, we will utilize generalized

linear mixed models (GLMM) to model the probability of opioid use across all time points (i.e. Day 7, 15, 30, and 90) as a function of study arm (ACU vs. OPI), time, the arm-by-time interaction, and randomization stratification variables.. For Aim 1 symptom burden, and for the continuous Aim 2 outcome measures, we will use linear mixed models (LMM) to similarly model those continuous endpoints over time. For both the GLMM and LMM analyses, we will use interaction terms between time and study arm to allow us to plot the arm-specific outcome trajectories over time. These statistical procedures (GLMM and LMM) account for within-subject correlations from repeated measurements in the same subjects and allow estimation of between-group differences without necessitating exclusion of participants with missing data.

**14.2.2. Specific Aim 1 Analysis Methods.** To test Aim 1 hypotheses, we will test whether ACU has fewer opioid users compared to OPI at Day 7 (Hypothesis 1a) and at Day 90 (Hypothesis 1b) using separate but similar logistic regression models. Each model will predict opioid use at the given time point as a function of treatment arm (ACU vs. OPI), controlling for the randomization stratification variables (study site and cancer diagnosis). To test whether ACU reduces symptom burden at Day 7 compared to OPI (Hypothesis 1c), we will use a LMM to model the baseline and Day 7 MDASI-BMT Total Symptom Severity scores as a function of study arm (ACU vs. OPI), time (Day 0 and Day 7), and the arm-by-time interaction (coefficient of interest), controlling for the randomization stratification variables.

**14.2.3. Specific Aim 2 Analysis Methods.** For the Aim 2 hypotheses we will first test (Hypothesis 2a) whether mean pain scores among ACU patients were non-inferior to those among OPI patients (within a non-inferiority margin of 0.34 standard deviations) at Day 7 (key Aim 2 endpoint) using a LMM containing arm, time (Days 0 and 7), and the arm-by-time interaction as predictors, controlling for the randomization stratification factors. That is, if the mean Day 7 pain score in the ACU arm is not significantly ( $p < 0.025$ ) more than 0.34 standard deviations higher than the mean OPI pain score, then we will consider ACU to be non-inferior to OPI with respect to Day 7 pain control. A similar analysis will be performed for the Day 90 pain scores. For Hypothesis 2b, we will estimate mean differences (and 95% confidence intervals) between ACU vs. OPI side effect ratings, PROMIS-29 scores, and PROMS scores using separate linear mixed models for the Day 7 and Day 90 outcomes, controlling for the randomization stratification variables and baseline score (when relevant). We will have 80% power to detect unadjusted differences between study arms on these outcomes as small as 0.34 SD (i.e., Cohen's  $d = 0.34$ ) using two-sided tests and  $p < 0.05$ . By convention, this effect size is between a small (i.e.,  $d = 0.20$ ) and moderate ( $d = 0.50$ ) effect size. We will have power to detect smaller effect sizes in the covariate-adjusted regression analyses described above, but we have insufficient preliminary data on which to base estimates of these adjusted effect sizes.

We will adjust all comparisons between the two treatment arms for the randomization stratification factors - study site and primary cancer diagnosis (MM versus HD versus NHL) - by including them as fixed effects in our statistical models.

**14.2.4. Exploratory Aim 1, Mediation.** We will explore potential causal mechanisms by testing mediation hypotheses (e.g. test whether the effect of treatment on Day 90 opioid use is mediated through the effect of treatment on Day 7 opioid use). We will use the approach to testing mediation hypotheses outlined in Imai, Keele, & Tingley (2010) in which a series of models are fit that allow estimation of the total, direct, and indirect (i.e., through the mediator) effects of treatment arm on Day 90 opioid use.

**14.2.5. Exploratory Aim 2, Heterogeneity of Treatment Effect (HTE).** We expect patients will respond differently to study interventions but we do not have enough preliminary data to generate hypotheses. Our HTE analyses will be exploratory and hypothesis-generating. We will explore whether sex, race, ethnicity, gender, primary cancer diagnosis (MM versus HD versus NHL), Opioid Risk Tool (ORT), Acupuncture Expectancy Scale (AES) score, or concurrent use of other medications with analgesic effects influence response to interventions in this population. We will add these variables and variable-by-arm interaction terms to our Day 7 and Day 90 logistic and linear regression models to identify potential patient-level factors associated with differential responses to treatment with respect to our primary and secondary outcomes. Each variable of interest will be assessed for HTE in a separate model. We will guard against inflated type I errors due to multiple testing by adjusting the variable-by-intervention interaction p-values for the false discovery rate. We intend to approach the evaluation of HTE based on existing literature and patient/clinician input. Our current focus on evaluating and reporting HTE will be based on the approach proposed by Kent et al. However we will also apply promising emerging Bayesian and machine learning methods, which can identify HTE and subgroups based on multiple variables simultaneously and are potentially more powerful than traditional univariate methods. We recognize that these types of sub-group analyses, although patient-centered, may need to be interpreted with caution and cannot replace the primary analyses.

**14.3. Missing Data.** We will first explore whether missingness is associated with observed variables (particularly randomization arm and the baseline outcome measures) by comparing patients with complete and incomplete data. Of note, our general longitudinal data analysis approaches described above (GLMM and LMM) validly include patients with incomplete data under the missing at random assumption. However, our exploration of the data may deem the missing at random assumption to be inappropriate, and not all our hypotheses will be tested using these longitudinal modeling approaches. In these cases, we will use well-established methods such as multiple imputation and pattern mixture models to help us deal with these issues. We will perform sensitivity analyses to evaluate the robustness of our main findings by using multiple imputation to impute the missing outcomes (particularly for Day 7 and Day 90) and duplicating the analyses using the multiply imputed data sets.

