Autologous hematopoietic stem cell transplantation (auto-HSCT) is a treatment for multiple myeloma (MM), Hodgkin disease (HD), and non-Hodgkin lymphoma (NHL). Patients receive high-dose chemotherapy (HiChemo) followed by infusion of hematopoietic stem cells days later. Pain is rated one of the top five symptoms during this treatment. Oral mucositis from HiChemo is the main source of severe acute pain and the main reason patients are initiated on opioids. Between 30-43% of patients undergoing HiChemo and auto-HSCT experience severe (grade 3 or 4) mucositis which creates distress and interferes with eating and drinking. Mucositis pain follows a predictable course, usually starting shortly after HiChemo and peaking around day 7 after initiation of HiChemo. It begins to subside around days 15, and has usually resolved by Day 30. By Day 90, there should be no residual pain caused directly by HSCT. The pain can lead to periods of difficulty eating, malnutrition, dehydration, weight loss, depression, and impaired quality of life. Opioids are usually used to manage the pain. Although effective, opioids are often associated with side effects like constipation, nausea, sedation, and delirium. After mucositis has subsided, some patients may have become accustomed to opioids and use them chronically for other pain. The intensity of pain during HiChemo, the high incidence of opioid use in this population, and the predictable clinical course make HiChemo/HSCT an excellent model to study the effects of pain control interventions during cancer treatment on short- and long-term opioid use.

Pain management during cancer treatment presents patients and clinicians with a decision dilemma. The Joint Commission, American College of Physicians (ACP), National Comprehensive Cancer Network (NCCN) and American Society of Clinical Oncology (ASCO) guidelines all recommend a combination of pharmacologic (mainly opioids during HiChemo) and non-pharmacologic modalities. However there is currently no strong evidence guiding clinicians or patients on how to combine non-pharmacologic and pharmacologic interventions to manage the pain patients experience during cancer treatment. In particular, there is a lack of evidence that considers what patients perceive as important, e.g. side effects and risk of long-term opioid use.

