## 7.2 Randomization

After registration, research staff will randomize patients via MSK's secure Clinical Research Database (CRDB) using permuted blocks of random length. The allocation ratio will be 1:1 for ACU:OPI. Using the institutional randomization standard procedure with random blocks for RCTs will ensure full allocation concealment. Randomization will be stratified by study site, primary cancer diagnosis (MM versus HD versus NHL) and transplantation setting (inpatient versus outpatient) to ensure these characteristics are comparably distributed between the two study arms.

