## 9.0 PRE-TREATMENT/INTERVENTION

Enrolled patients will receive the following baseline assessments within 4 weeks before the first dose of HiChemo. Detailed descriptions of each assessment are in Section 11.0 and 13.1.

- Demographic and Clinical Features
- Symptom Burden (MDASI-BMT), paper or electronic
- Brief Pain Inventory – Short Form (BPI), paper or electronic
- Patient-Reported Oral Mucositis Symptom Scale (PROMS) ,paper or electronic
- Pain Medication Side Effects Questionnaire,paper or electronic
- Quality of Life (PROMIS-29), paper or electronic
- Adverse Events (CTCAE v5)
- Opioid Risk Tool (ORT), paper or electronic
- Acupuncture Expectancy Scale (AES), paper or electronic

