to screen for opioid misuse risk, and takes 2 minutes to complete. This data will be collected at baseline and used in Heterogeneity of Treatment Effect (HTE) analysis to assess whether it influences the effects of acupuncture. Expectancy for acupuncture may influence its clinical effects. We will assess patients at baseline using the Acupuncture Expectancy Scale (AES). This is a validated instrument (takes about 3 minutes to complete) with an internal consistency (Cronbach's  $\alpha$ ) of 0.95 and test-retest reliability of 0.62 over four weeks without acupuncture treatment. This data will be used as a variable in HTE analyses for predictor to response and sensitivity analyses. We will also track use of healthcare resources, such as the length of hospital stays and transfers to the intensive care unit during HSCT, and emergency room visits and readmission during the first 30 days post-HSCT. These are exploratory endpoints to generate preliminary data about impact on the health care system, e.g. iatrogenic adverse events from opioids and delayed discharge from opioid side effects.

All patient-reported measures will be administered either electronically (on a tablet if in clinic, via secure link if at home) or on paper.

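### The primary opioid-use models omit the baseline pain and opioid-risk scores scheduled for every enrolled patient; adding them could gain about 0 to 6 points of Day 90 power

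*Combined protocol and SAP*

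**What the plan says.** Section 14.2.2 sets out one logistic model for opioid use at Day 7 and one for Day 90. It says "Each model will predict opioid use at the given time point as a function of treatment arm (ACU vs. OPI", and describes the remaining terms as "controlling for the randomization stratification variables (study site and cancer diagnosis". The end of Section 14.2.3 repeats the two factors, gives diagnosis as MM, HD or NHL, and says the adjustment is made "by including them as fixed effects in our statistical models". No other covariate is named for these models.

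Section 9.0 lists, among the baseline assessments for enrolled patients, "Brief Pain Inventory – Short Form (BPI), paper or electronic" and "Opioid Risk Tool (ORT), paper or electronic". The schedule in Section 11.0 marks both at baseline. Of the ORT, Section 13.1 says "This data will be collected at baseline and used in Heterogeneity of Treatment Effect (HTE) analysis", and Section 14.2.5 places it in exploratory interaction models. Baseline BPI appears in no opioid-use model.

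Other analyses do use baseline scores. The symptom-burden and pain models carry the baseline value as a repeated measure, and the Hypothesis 2b models adjust for it where relevant. Section 14.2.3 notes that covariate adjustment allows smaller effects to be detected, but says so only of those Aim 2 outcomes.

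**The concern.** The two opioid endpoints carry 0.04 of the total alpha of 0.05, and Day 90 opioid use alone set the sample size (Section 14.1). Planned power is 81%, so there is little reserve. When a baseline variable predicts the outcome, including it in a logistic model raises the power of the arm test without extra patients or alpha.

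A pain score and a screen for opioid-misuse risk are natural candidates. Section 4.2 says opioids are started and adjusted by pain level, and Section 3.0 says that later "some patients may have become accustomed to opioids and use them chronically for other pain". Eligibility (Section 6.1) excludes regular opioid use but not pain, so baseline pain can still vary. At stake is a modest amount of power on the endpoint that sized the trial, available from data already being collected.

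**Working it through.** **Inputs from the documents.** 300 randomised 1:1, 10% attrition, so n = 135 evaluable per arm; Day 90 rates 25% (OPI) and 10% (ACU); two-sided alpha 0.02, z = 2.326; stated power 81% (Section 14.1).

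**Step 1: reproduce the stated power with no covariates.**
- Pooled two-proportion test: SE under the null = √(2 × 0.175 × 0.825 / 135) = 0.0462. SE under the alternative = √((0.25 × 0.75 + 0.10 × 0.90) / 135) = 0.0453. Power = Φ((0.15 − 2.326 × 0.0462) / 0.0453) = 82.5%.
- Wald test on the log odds ratio: ln 3 = 1.099. SE = √(1/(135 × 0.1875) + 1/(135 × 0.09)) = 0.349. Power = Φ(1.099/0.349 − 2.326) = 79.4%.
- Unpooled variance gives 83.7%.

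The stated 81% lies within these variants, so it takes no credit for covariates and does not depend on them.

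**Step 2: add a baseline prognostic index.** One standard-normal index stands for baseline pain and ORT together. Marginal rates are held at 25% and 10%, with 135 per arm, a Wald test at two-sided 0.02 and 10,000 simulated trials per setting. The odds ratios per SD are assumptions, because the documents give none.

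| Assumed odds ratio per SD | Power without index | Power with index | Gain (points) | Conditional arm odds ratio |
|---|---|---|---|---|
| 1.0 | 82.7% | 82.4% | −0.3 | 0.33 |
| 1.3 | 82.2% | 82.5% | 0.3 | 0.33 |
| 1.5 | 82.5% | 83.2% | 0.7 | 0.33 |
| 2.0 | 82.0% | 84.8% | 2.8 | 0.31 |
| 2.5 | 82.3% | 86.9% | 4.6 | 0.29 |
| 3.0 | 82.8% | 88.5% | 5.7 | 0.28 |

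The Monte Carlo standard error of one power figure is √(0.83 × 0.17 / 10,000) = 0.4 points, so the first row is no change. At the plan's more favourable 30% versus 10%, the gain is at most about 2 points (96.8% to 98.6% at 3.0 per SD).

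**Step 3: use two separate scores.** With separate, independent scores of odds ratio 1.8 and 1.5 per SD (4,000 trials), power moves from 83.0% to 85.5%. The combined strength is exp(√(ln²1.8 + ln²1.5)) = exp(√(0.345 + 0.164)) = 2.04 per SD. The gain of 2.5 points agrees with the 2.8 points at 2.0 above.

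**Step 4: compare with the planned model.** Steps 2 and 3 compare against a model with arm only, whereas the plan already adjusts for site and diagnosis. With those terms in both models, adding the two scores moves power as follows:
- no prognostic value: 83.4% to 83.2%;
- odds ratios 1.5 and 1.3: 83.1% to 84.4%;
- odds ratios 2.2 and 1.5: 82.5% to 86.3%.

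The gain over the planned model is of the same size.

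**Step 5: can the model carry the terms?** Expected Day 90 users = 135 × 0.25 + 135 × 0.10 = 33.75 + 13.5 ≈ 47. Parameters are arm 1, site 1, diagnosis 2 and scores 2, making six, or 47/6 ≈ 8 events each. A transplantation-setting term would make seven (47/7 ≈ 7). Step 4 shows no material loss of power from the added terms.

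**Step 6: express the gain in patients.** At 2.0 per SD, the ratio ((2.326 + 1.028)/(2.326 + 0.915))² = 1.07, where 1.028 and 0.915 are the normal quantiles of 84.8% and 82.0%. That is worth about 7% more evaluable patients, or 0.07 × 270 ≈ 19.

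**The case against.** The strongest reply is that nothing in the documents shows either score to be prognostic, and the population gives reason for doubt. Regular opioid users are excluded, and Section 6.0 says the target is chemotherapy-induced pain and not severe pre-existing pain. Section 3.0 names mucositis after chemotherapy as the main reason opioids are started, while baseline BPI may be taken up to four weeks earlier. The Section 4.2 text concerns pain during transplantation, and the Section 3.0 sentence on chronic use concerns habituation after exposure; neither is about baseline pain. The ORT screens for misuse risk, which differs from receiving any opioid for mucositis. All of this stands, and it is why the gain may be near zero.

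Adjustment also has a price. The arm odds ratio becomes conditional and moves from the marginal 0.33 used in planning to about 0.31 to 0.28 in the stronger scenarios, while Section 14.2.1 favours models that are simple to interpret. This stands, but a standardised risk difference answers it.

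A reader might infer that the models contain no patient-level predictor. They do: cancer diagnosis is one. A reader might also see a contradiction with the continuous-outcome models. Those adjust for the outcome's own baseline value, which for opioid use hardly varies because of eligibility, so the plan is not inconsistent.

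Finally, a reader might say that leaving the scores out makes the analysis of assessed patients invalid under dropout. Conditioning on them would let dropout depend on them, which is a side benefit. But Section 14.3 already plans to examine missingness against baseline measures and to repeat the analyses with multiple imputation.

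**Conclusion.** The point holds as a missed efficiency. Neither primary opioid-use model includes a baseline pain or opioid-risk score, although both are scheduled for all enrolled patients. Under assumed combined odds ratios of 1 to 3 per SD, including them would add about 0 to 6 points of Day 90 power: under 1 point up to 1.5 per SD and about 3 points at 2.0. If the scores are not prognostic, the cost is within simulation error.

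The documents do not support the stronger reading that the trial is underpowered or certainly loses power. The 81% figure reproduces without covariates. Nor do these results carry over to Day 7 as a number: only Day 90 scenarios were simulated, and Section 14.1 gives no Day 7 rates for this trial, only an expectation of similar or higher power. The planned analysis is valid as written.

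**What to change.** In Section 14.2.2, before any comparison of outcomes by arm:
- Add baseline BPI Worst Pain and baseline ORT score as prespecified covariates, each as a linear term, in both logistic models.
- State a simple rule for missing baseline scores, such as one value imputed from both arms pooled, so that no patient is dropped for a missing covariate.
- Report the standardised risk difference beside the arm odds ratio, and say that the odds ratio is conditional on the covariates.
- Keep the current model as a sensitivity analysis.

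In the same edit, reconcile the list of stratification factors. Section 7.2 says "Randomization will be stratified by study site, primary cancer diagnosis (MM versus HD versus NHL) and transplantation setting (inpatient versus outpatient", but Sections 14.2.2 and 14.2.3 name only site and diagnosis.

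The cost is SAP wording only, because the data are already scheduled. The remaining downside is that the conditional odds ratio lies further from the planning value of 0.33, so the power statement should make clear that 0.33 is marginal.
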